3.8. Administration of Study Medication

Study medication will be administered SC during onsite visits (Visits 2, 4, 5, and 6) on Study Day 1 (Week 0), Day 29 (Week 4), Day 57 (Week 8), and Day 85 (Week 12).

The dosing regimens are illustrated in the following diagram:

NOTE: MFNS will be provided to all subjects as standard of care for all 3 groups.

Abbreviations: MFNS=Mometasone Furgate nasal spray, SC=subcutaneous

Subcutaneous injection sites should be alternated among upper arms or, if necessary, the different quadrants of the abdomen (avoiding navel and waist areas). If possible, the same site should not be injected for 2 consecutive months. Study drug should be administered only into areas of normal-looking skin; if possible, Study Day 1 (loading dose) injections should be administered in separate upper arms. If both injections are administered in the same area, the injections should be spaced approximately 2 inches apart. Additional detail will be located in the Pharmacy Manual.

Statistical Analysis Plan for Interventional Studies Sponsor: Anaptys Bio Inc.; Protocol No.: ANB020-006

3.9. Study Procedures and Flowchart

Table 1: Schedule of Activities

Phase	Screening			Trea	tment	Safety Follow-Up			
Week	-4 to 0	0	1ª	4	8	12	16/EOT	20	24/EOS/ETV
Study Day	-31 to -20*	1d	5± 1d	29±3d	57±3d	85±3d	113±5d	141±5d	169±5d
Visit	1	2	3	4	5	6	7	8	9
Informed Consent	х								
IXRS: Subject Screening/Randomization/Drug Dispensing/Treatment Completion	х	х		х	х	х	х		
Inclusion/Exclusion Criteria	х	х							
Medical History (Including Prior CRSWNP, Therapy)	х								
Height	х								
Physical Examination:	х	х					х		х
Vital Signs Including Weightd	х	х		х	х	х	х	х	Х
12-Lead ECG:	х	х					х		Х
Follicle Stimulating Hormone	х								
Pregnancy Tests	х	х		х	х	х	х	х	х
Drugs of Abuse (urine), HIV, Hepatitis B and C Viral Testing, TB Test (QuantiFERON $^{\circ}$ Gold) ^h	х								
Hematology, Chemistry	х	х	х	х	х	х	х		Х
Urinalysis	Х	х					х		Х
Study Drug Injection		х		х	х	х			
Pharmacokineticst		Х	х	х	х	х	х	х	х
Immunggenicity.		х		х	х	х	х	х	х
FE[V1 (Spirometry) ^m		XX		х	х	х	х		

Statistical Analysis Plan for Interventional Studies

Sponsor: Anaptys Bio Inc.; Protocol No.: ANB020-006

Phase	Screening			Trea	tment			Safet	y Follow-Up
Week	-4 to 0	0	1ª	4	8	12	16/EOT	20	24/EOS/ETV
Study Day	-31 to -20*	1d	5± 1d	29±3d	57±3d	85±3d	113±5d	141±5d	169±5d
Visit	1	2	3	4	5	6	7	8	9
ePRO Device Dispensation/Collection		Х							х
NPIF readings collected via Diary	<							··· ·· ··	\rightarrow
Adverse Event Monitoring		 						>	
Concomitant Therapy	· · · ·		tan t	0				al a second	→
Nasal Endoscopy (centralized Nasal Polyp Score) ^{b, w}	x	Х		х	х	X	х		х
CT Scan (Lund & 3D- correct accordingly) ^x		х					x		
Smell Test (UPSIT)9		Х			х	-	x		
SNOT-22	x	х		х	х	х	х		х
Visual Analogue Scale (VAS)					X (Wee	ekly via eP	Q Device)		
QoL (SF-36, EQ-5D)		х		х	х	х	х		х
Nasal Polyps Related Resource Questionnaire		х		х	х	х	х		х
ACQ-7 ^r		х		х	х	х	х		х
Nasal Polyp Biopsies ^{s, t}		х					х		
Stored DNA Sampling ^{t, u}		х							
Whole Blood RNA Sampling		х		Х			х		х
MFNS – distribute and verify usage	<		- Chi - Chi	с — Л	r	-11 ⁻	0.0	-15	

Abbreviations: ACQ-7 = 7-item Asthma Control Questionnaire; CRSwNP = Chronic Rhinosinusitis with Nasal Polyposis; d = day(s); CT = computed tomography; DNA = deoxyribonucleic acid; ECG = electrocardiogram; EOS = End of Study; ePRO = electronic patient-reported outcome; EQ-5D = EuroQol-5D for measuring QoL; ETV = Early Termination Visit; HIV = human immunodeficiency virus; IXRS = Interactive Web Response System; NPIF = nasal peak inspiratory flow; QoL = quality of life; SF-36 = Short Form-36 Health Assessment; SNOT-22 = Sino-Nasal Outcome Test; TB = tuberculosis; UPSIT = smell identification test; VAS = visual analogue scale.

- * During the screening window patients must use MFNS for a minimum of 20 days prior to Day 1 (maximum screening window is 31 days). Screening procedures can be conducted up to Day -1 if necessary.
- ^a Visit must occur 5 days (±1 day) after Visit 2.
- ^b Inclusion/exclusion criteria are based on all screening assessments, Visit 1 nasal endoscopy, and laboratory results. Week 0/Day 1 pre-dose assessments are to be reviewed before enrollment.
- ^c A complete physical examination will be performed at the screening visit. All other physical examinations should be abbreviated and address associated complaints or findings and any other assessments required to evaluate adverse events.
- ^d Vital signs assessments should be performed before blood sampling and before injection of study drug at each study visit where administered. Blood pressure readings should be obtained after approximately 15 minutes of rest in a seated position.
- ^e 12-Lead ECG should be performed after 10 minutes of rest in a supine position and before the blood sample is collected. ECG must be conducted on ECG machine provided by ERT for the ANB020-006 clinical trial.
- ^f Follicle stimulating hormone may be used to confirm menopausal status in female subjects as needed.
- ^g Pregnancy testing is only required for women of childbearing potential (WOCBP). A serum test will be performed at the screening visit; urine pregnancy tests will be performed at treatment and follow-up visits. Testing must be performed before injection of study drug at Weeks 0, 4, 8, and 12. A negative result must be obtained at Visits 1 and 2 before subject may be randomized.
- ^h HIV 1 and 2, hepatitis B surface antigen, hepatitis B core antibody, hepatitis C antibody, and *Mycobacterium tuberculosis* (TB) will be assessed. Subjects with an indeterminate QuantiFERON® TB Gold result at Screening will be allowed 1 retest.
- ⁱ Hematology and chemistry: Blood samples will be taken before injection of study drug, after the ECG and vital signs assessments.
- ^j Subject is required to remain onsite for 2 hours post-dose for observation at Week 0 (Day 1). Subjects with any ongoing treatment-emergent AEs or SAEs at the time of scheduled discharge from the study center should remain at the study center until the Investigator has determined that these events have been resolved or deemed as not clinically significant. Subjects are not required to remain onsite after follow-up injections (Weeks 4, 8, and 12) unless deemed necessary by the Investigator, if there have been injection site reactions, or other AEs are noted.
- ^k Pharmacokinetics blood samples will be collected for all subjects at the following time points:
 - Visit 2/Week 0: prior to dosing on Day 1.
 - Visit 3/Week 1: Visit 3 can occur 3 to 5 days after Visit 2.
 - Week 4, 8, 12: prior to dosing.
 - Week 16, 20, and 24: any time at each visit.
- ¹ Immunogenicity blood samples will be collected for all subjects at the following time points:
 - Visits 2 (Week 0), 4 (Week 4), 5 (Week 8), and 6 (Week 12): prior to dosing.
 - Visits 7 (Week 16), 8 (Week 20), and 9 (Week 24): any time at each visit.
- ^m All subjects should have the result of FEV₁ (% of predicted normal as defined by the Global Initiative for Asthma) recorded in the source on Day 1 and at all the other scheduled visits during the treatment period. Every effort should be made to perform FEV₁ assessment at the same time at each visit. If a subject with active asthma's FEV₁ \leq 60% on Day 1, then the subject will not be randomized. FEV₁ assessment should be conducted on the spirometry machine provided by ERT for the ANB020-006 clinical trial.

- ⁿ The ePRO device will be provided to subjects on Day 1 upon confirmation of randomization. Subjects should be trained on log in and completion of NPIF distribution within the ePro device. The subjects should bring the ePRO device to each visit. The ePRO device should be returned to the site at the Week 24 (EOS) visit. Detailed instructions will be provided separately in the Procedures Manual.
- Peak Nasal Inspiratory Flow Meters will be provided to patients during the screening visit and patients will be instructed on use and recording requirements. NPIF values will be recorded on a paper diary during Screening (for 1 week/7 consecutive days). Diary must be returned to the study coordinator at the Day 1 dosing visit. Following randomization, eDiaries will be distributed and NPIF values will be recorded directly in the device.
- ^p Concomitant therapy will include pharmacologic and nonpharmacologic therapies.
- ^q Testing must be performed before injection of study drug at Weeks 0 and 8.
- ^r The ACQ-7 will be assessed only in subjects with an active asthma disease.
- ^s Optional polyp biopsies will be collected from subjects who indicate approval on ICF, in study centers with the capability to conduct the procedure.
- ^t Samples will be collected before injection of study drug on Day 1.
- ^u Optional sampling for exploratory analysis of DNA and RNA, requiring separate pharmacogenetic consent acknowledgment in ICF.
- ^v MFNS bottles will be distributed and used bottles collected at monthly visits to assess use. Subjects should be approximately 80% compliant with usage during Screening and throughout the study. During Screening subjects must complete a minimum of a 20 day run-in using MFNS prior to Day 1.
- Endoscopy can utilize study windows to ensure procedure can be completed prior to dosing. Day 1 Endoscopy can occur up to 5 days prior to Day 1 clinic visit. If endoscopy is performed on site it should be completed after all other study assessments are done and prior to dosing on dose days.
- X Day 1 CT must be collected prior to dosing on Day 1. If necessary, the Day 1 CT can be collected during Screening, prior to Day 1, however all efforts should be made to conduct CT after subject screening labs have been reviewed and it is determined subject is likely eligible for the study. Note: CTs collected within 3 months prior to randomization (Day 1) can be utilized in lieu of a new Day 1 CT if the necessary imaging requirements are present.
- ^y Day 1 spirometry should be assessed prior to randomization to ensure inclusion/exclusion criteria are met

4. ENDPOINTS

4.1. Primary Efficacy Endpoint

Associated with the primary efficacy objective to evaluate the efficacy of etokimab compared to placebo in subjects with CRSwNP following a 16-week treatment period are the following two co-primary endpoints:

- Change from baseline to Week 16 in bilateral endoscopic Nasal Polyp Score (NPS)
- Change from baseline to Week 16 in Sino-Nasal Outcome Test (SNOT-22) scores

4.2. Secondary Efficacy Endpoints

Secondary endpoints identified in the protocol are listed below:

- Time to first response (≥ 1 point improvement) in NPS
- NPS response defined as a reduction of at least 1.0 from baseline to Week 16 in NPS
- SNOT-22 response defined as a reduction of at least 12.0 from baseline to Week 16 in SNOT-22
- Change from baseline to Week 16 in sense of smell as assessed by the University of Pennsylvania Smell Identification Test (UPSIT)

4.3. Exploratory Endpoints

Exploratory endpoints identified in the protocol are:

4.3.1. Quality of Life (QoL)

- 36-item Short Form Health Survey (SF-36)
- European QoL scale (EQ-5D)
- Patient-related rhinosinusitis symptoms severity using a visual analog scale (VAS)
- Number of nocturnal awakenings

4.3.2. Other effects

- Percent change from baseline to Week 16 in sinus opacification as assessed by CT scan using Lund-Mackay score
- Change from baseline to Week 16 in Nasal peak inspiratory flow (NPIF)
- Change from baseline to Week 16 in NPS in subjects with comorbid asthma
- Change from baseline to Week 16 in SNOT-22 scores in subjects with comorbid asthma
- Percent change from baseline in 3-dimensional volumetric measurement of the maxillary sinus as assessed by CT scan
- Change from baseline to Week 16 in forced expiratory volume (FEV1) (overall and in subgroup with asthma)

- Change from baseline to Week 16 in FEV1 percent of predicted (overall and in subgroup with asthma)
- 7-Item Asthma Control Questionnaire (ACQ-7) in asthma subgroup
- Reduction of eosinophils (blood eosinophil count) from baseline (Day 1 pre-dose) to Week 16
- Time to study treatment discontinuation
- Incidence of treatment discontinuation due to need for OCS or nasal polyp surgery
- Change in Nasal Polyp Resource Questionnaire from baseline to Week 16

4.4. Pharmacokinetic Endpoints

Pharmacokinetic endpoints are as follows:

A limited sampling strategy to collect samples of whole blood was implemented for the determination of etokimab concentrations in human serum for PK assessment following subcutaneous (SC) administration.

The PK endpoints for this study are as follows:

- Primary PK parameters
 - Apparent clearance (CL/F) of etokimab
 - Apparent volume of distribution (Vd/F) of etokimab
- Secondary PK parameters
 - Area under the curve (AUC_{τ}) for the first and last dose
 - Maximum concentration (C_{max}) for the first and last dose
 - T_{max} (Time of maximum concentration) for the first and last dose
 - $t_{1/2}$ (apparent terminal half-life) for the last dose after SC dosing if possible

4.5. Safety Endpoints

Outcome measures are listed below:

- Incidence of adverse events (AEs) and treatment-emergent AEs (TEAEs)
- Incidence of serious adverse events (SAEs)
- Changes in clinical laboratory tests (hematology, chemistry, and urinalysis)
- Changes in vital signs (blood pressure [BP], temperature, respiration rate, and pulse rate [PR])
- Changes in electrocardiogram (ECG) parameters
- Immunogenicity (anti-drug antibody [ADA] and neutralizing ADA)

5. ANALYSIS SETS

5.1. Enrolled Set

The Enrolled Set will include all subjects who gave informed consent and were enrolled in the study. Unless specified otherwise, this set will be used for subject listings and summaries of subject disposition.

5.2. Safety Analysis Set

The Safety Analysis Set will include all randomized subjects who receive at least 1 dose of etokimab or placebo. The Safety Analysis Set will be used for all safety analyses. Subjects will be analyzed according to treatment received. Unless specified otherwise, this set will be also used for subject listings and summaries of safety endpoints.

5.3. Full Analysis Set

The Full Analysis Set (FAS) will include all randomized subjects who receive at least 1 dose of etokimab or placebo and have baseline and at least 1 post baseline NPS and/or SNOT-22 scores up to Week 16. Subjects will be analyzed according to randomized treatment. Unless specified otherwise, this set will be also used for subject listings and summaries for all efficacy analyses.

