9.3 ANALYSIS SETS

The analysis sets for evaluating the efficacy, safety, and pharmacokinetics of etokimab are defined in Table 2.

Table 2. Analysis Sets

Analysis Set	Description
Safety Analysis Set	The safety analysis set will include all randomized subjects who receive 1 dose of etokimab or placebo. The safety analysis set will be used for all safety analyses. Subjects will be analyzed as treated.
Full Analysis Set	The full analysis set (FAS) will include all randomized subjects who receive 1 dose of etokimab or placebo and have baseline and at least 1 post baseline NPS and/or SNOT-22 scores up to Week 16. The full analysis set will be used for all efficacy analyses. Subjects will be analyzed as randomized.
PP Analysis Set	The PP (Per Protocol) analysis set will include all subjects in the FAS analysis set who do not have major protocol violations that would affect the evaluation of the primary efficacy endpoints.
PK Analysis Set	The PK analysis set will include all subjects in the safety analysis set who have at least one quantifiable postdose PK sample available and who do not have events or protocol deviations or events with the potential to affect PK concentrations. The PK analysis set will be used for all PK analyses.

Abbreviations: FAS = Full analysis set, PP = Per protocol, PK = Pharmacokinetics.

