9.4.2.2 ANALYSIS OF THE SECONDARY AND EXPLORATORY ENDPOINT(S)

Analysis of secondary efficacy endpoints will be performed in a hierarchical order as listed in Section 3 to adjust for statistical multiplicity. More details for multiplicity adjustment will be described in SAP.

For the secondary PK endpoints, primary PK parameters of CL/F and volume of distribution will be estimated by population PK modeling from ANB020 serum concentrations after SC administrations. Secondary PK parameters of AUC_{tau}, C_{max}, t_{max}, for the first dose and AUC_{tau}, C_{max}, t_{max} and T_{1/2} for the last dose will also be calculated for ANB020 after SC administrations, where possible, using a Bayesian post-hoc estimation approach based on the aforementioned population PK model. Other parameters may be evaluated, if needed. The PK parameters will be listed and summarized using appropriate descriptive statistics. Pharmacokinetic concentration data collected from the study may be included in a population PK based (meta) analysis, using non-linear mixed effects modeling. The data from this study may be combined with data collected from other studies for population PK model development. A covariate screen of subject specific factors (eg, demographic and clinical characteristics) will be included in the analyses. Any population PK analysis plan will be described in detail in a pharmacometric analysis plan.

All secondary and exploratory efficacy analyses will be performed on the FAS. Table 3 includes a summary of the statistical methods to be used in analyzing efficacy endpoints (co-primary, secondary, and exploratory). Full details of statistical analysis for all secondary and exploratory endpoints will be provided in the SAP.

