8. EFFICACY

The primary efficacy objective of this study is a comparison of each of two dosing regimens of etokimab with placebo in the treatment of subjects with CRSwNP following a 16-week treatment period (change from baseline using co-primary endpoints). Two co-primary efficacy endpoints will be analyzed.

The analysis of the primary and secondary efficacy parameters will be performed on the FAS, unless otherwise noted. The primary and secondary efficacy analyses will be repeated on the PP analysis set if there are substantial differences between the makeup of the FAS and the PP Analysis Set, in order to assess the impact of major protocol deviations on the key inference.

All primary and secondary efficacy variables will be analyzed for data obtained for the Treatment Period.

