Completers analysis: An Analysis of Covariance (ANCOVA) will be employed for Week 16 NPS for subjects who completed Week 16 only, where the change from baseline at Week 16 is modeled with baseline NPS score as covariate and treatment as a factor.

All primary and supplementary statistical analyses will be performed for the Full Analysis Set. If the Full Analysis Set and the Per Protocol Analysis Set differ by more than 10 subjects, the primary analysis of NPS will be repeated for the Per Protocol Analysis Set.

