8.2.2. Responder Analysis: Week 16 NPS Score Decrease of ≥1 from Baseline

One of the (co)primary endpoints is the change from baseline in NPS score at Week 16. For this variable, a responder may be defined as a subject whose NPS score at Week 16 decreased from baseline by at least 1.0. If

the subject did not make it to Week 16, or if the subject did not achieve an NPS score reduction ≥ 1 , the subject will be deemed a "Non-responder" (Response='No').

Summary statistics for each treatment group will include the number (n) and percentage (%) of subjects who responded, and an exact confidence interval for the % responders.

A logistic regression will be employed with terms for treatment (3 levels: 1=Placebo, 2=Eto Q8W, 3=Eto Q4W), baseline as a continuous covariate, and stratification factor (asthma comorbidity:1=Yes, 0=No).

Using the logistic regression model, for each comparison of the etokimab groups with the Placebo group, the estimated odds ratio for the etokimab versus placebo odds of response, a 95% Confidence Interval for the odds ratio, and the p-value for that comparison will be displayed in the summary table.

It is expected that treatment with etokimab should lead to a greater odds of response vs. not responding, when compared to the Placebo group. A statistically significantly greater odds ratio for the etokimab vs. placebo group comparison will be taken as evidence of efficacy in favor of etokimab.

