8.2.3. Responder Analysis: Week 16 SNOT-22 Score Decrease of ≥ 12 from Baseline

The second co-primary endpoint is the change from baseline in SNOT-22 score at Week 16. For this variable, a responder may be defined as a subject whose SNOT-22 score at Week 16 decreased from baseline by at least 12. This cutoff point is based on the minimal clinically important difference (MCID) value reported by Phillips et al. (2018) and Phillips et al. (2019). If the subject did not make it to Week 16, or if the subject did not achieve an SNOT-22 score reduction \geq 12, the subject will be deemed a "Non-responder" (Response='No').

Summary statistics for each treatment group will include the number (n) and percentage (%) of subjects who responded, and an exact confidence interval for the % responders.

The same logistic regression as the responder analysis for NPS score will be employed for SNOT-22. It is expected that treatment with etokimab should lead to a greater odds of response vs. not responding, when compared to the Placebo group. A statistically significantly greater odds ratio for the etokimab vs. placebo group comparison will be taken as evidence of efficacy in favor of etokimab.

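### Dosed subjects with no post-baseline NPS or SNOT-22 score drop out of the responder analyses instead of counting as non-responders

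*SAP*

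**What the plan says.** **Who is analysed.** SAP 5.3 admits to the FAS randomised subjects who had at least one dose and who "have baseline and at least 1 post baseline NPS and/or SNOT-22 scores up to Week 16". Protocol 9.3 defines the set in the same way and adds: "The full analysis set will be used for all efficacy analyses". For the secondary endpoints, Protocol 9.4.2.2 states: "All secondary and exploratory efficacy analyses will be performed on the FAS". SAP Section 8 agrees: "The analysis of the primary and secondary efficacy parameters will be performed on the FAS, unless otherwise noted". Sections 8.2.2 and 8.2.3 name no other set.

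**How they are classified.** SAP 8.2.2 makes a subject a non-responder if "the subject did not make it to Week 16, or if the subject did not achieve an NPS score reduction" of at least 1 point. SAP 8.2.3 has the parallel rule for SNOT-22: "If the subject did not make it to Week 16, or if the subject did not achieve an SNOT-22 score reduction" of at least 12 points, the subject is a non-responder. Neither section makes an exception for subjects who leave very early.

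**When scores are taken.** In the Schedule of Activities (Protocol 1.3, SAP 3.9) the first scheduled post-baseline NPS and SNOT-22 are at Week 4. The Week 1 visit has neither. The Week 24/EOS/ETV column has both. Protocol 7.1 asks subjects who stop treatment to attend an early termination visit within 30 days of the last dose. SAP 6.4 maps that visit by study day, and Table 2a assigns Days 2 to 42 to Week 4.

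**The concern.** A subject who is dosed on Day 1 and leaves without giving either score did not reach Week 16, so the rule in 8.2.2 and 8.2.3 would make that subject a failure. The FAS condition removes the subject before the rule can apply. A subject who leaves just after a Week 4 assessment counts as a failure. One who leaves just before it, and gives no score afterwards, does not count at all.

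The exclusion depends on what happens after the first injection. If it differs between arms, the response rates and odds ratios no longer compare the randomised groups.

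The model gives no reason for it. Such a subject has no response data to offer a repeated-measures model, so the FAS condition costs the co-primary analyses nothing. The logistic models need only treatment, baseline score and asthma stratum. Baseline is the last value on or before first dose (SAP 8.1.1, 8.1.2), NPS and SNOT-22 are both used for eligibility at screening, and asthma status is needed for stratified randomisation. These should exist for essentially everyone dosed.

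The endpoints are second and third in the secondary hierarchy (SAP 8.2), where a p-value of 0.05 or more stops the interpretation of later endpoints.

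**Working it through.** **The plan's own figures.** No power or response rate is given for the responder endpoints. The planned size reproduces: 27/(1 − 0.18) = 32.9, rounded up to 33 per arm. For the co-primaries at n=27, a noncentral t calculation gives 87.8% for NPS (difference 1.3, SD 1.5; stated 87%) and 92.5% for SNOT-22 (difference 18.1, SD 19.2; stated 92%). These figures are sound but do not bear on this point. They supply only the 33 per arm and a ceiling: 33 × 0.18 = 5.9, so at most about 6 per arm if every case of planned dropout or missing data lacked any post-baseline score.

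**Is there a route back in?**
1. After a single Day 1 dose, a termination visit within 30 days falls by about Day 31, inside the Week 4 window of Days 2 to 42. A usable NPS or SNOT-22 there puts the subject in the FAS, as a non-responder on both endpoints.
2. Because of the and/or in SAP 5.3, one of the two scores is enough.
3. A subject with neither score is not restored anywhere. SAP Section 5 has no all-randomised or all-dosed efficacy set. The supplementary analyses concern the co-primaries only and use the same set: "All primary and supplementary statistical analyses will be performed for the Full Analysis Set".

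**Effect on one arm's rate.** Let r be the responders among 33 dosed, and k the dosed subjects with no post-baseline score on either instrument. All-dosed rate = r/33; FAS rate = r/(33 − k); ratio = 33/(33 − k). Both r and k are assumptions.

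| k | Ratio | Overstatement, r = 8 to 20 |
|---|---|---|
| 1 | 1.03 | 0.8 to 1.9 points |
| 3 | 1.10 | 2.4 to 6.1 points |
| 6 (ceiling) | 1.22 | 5.4 to 13.5 points |

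**Effect on the comparison.** Assume 18/33 responders on active and 10/33 on placebo. The p-values are from an unadjusted chi-square test without continuity correction, not the planned logistic model.

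| Removed (active, placebo) | Active | Placebo | Difference | Odds ratio | p |
|---|---|---|---|---|---|
| None (all dosed) | 18/33 = 54.5% | 10/33 = 30.3% | 24.2 | (18/15)/(10/23) = 2.76 | 0.046 |
| 1, 1 | 18/32 = 56.3% | 10/32 = 31.3% | 25.0 | (18/14)/(10/22) = 2.83 | 0.044 |
| 2, 0 | 18/31 = 58.1% | 10/33 = 30.3% | 27.8 | (18/13)/(10/23) = 3.18 | 0.025 |
| 0, 2 | 18/33 = 54.5% | 10/31 = 32.3% | 22.3 | (18/15)/(10/21) = 2.52 | 0.072 |
| 3, 0 | 18/30 = 60.0% | 10/33 = 30.3% | 29.7 | (18/12)/(10/23) = 3.45 | 0.018 |
| 0, 3 | 18/33 = 54.5% | 10/30 = 33.3% | 21.2 | (18/15)/(10/20) = 2.40 | 0.091 |

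Equal removal of one per arm barely moves the contrast. Unequal removal of two or three moves it either way, and in this example removal on placebo takes p above 0.05.

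**The case against.** The strongest reply is that the plan is coherent as written. Protocol and SAP consistently name the FAS for efficacy; SAP Section 8 fixes the population, and 8.2.2 and 8.2.3 say how to classify subjects inside it. A reader might infer that the SAP contradicts itself, but the two rules can be applied together without conflict. What remains is a choice of population that sits badly with the non-responder rule.

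A reader might also infer that everyone who leaves before Week 4 is lost. The documents do not support that: the termination visit, the window mapping and the and/or condition keep any early leaver who gives one usable score. This stands and narrows the point considerably. It does not close it, because attendance is requested but cannot be guaranteed, and Protocol 9.4.2.3 accepts that missing data are inevitable.

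The consequence is also limited and partly visible. The two endpoints are interpreted only if the co-primaries and then time to first response succeed. SAP 7.1 summarises the number of subjects in each analysis set, so a reader could compare the Safety and FAS counts and largely rework the rates. That too stands, but a reworked rate is not a pre-specified analysis.

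**Conclusion.** The point holds in a narrow form. Dosed subjects with no post-baseline NPS and no post-baseline SNOT-22 at any visit up to Week 16 are excluded from both responder analyses on a post-randomisation criterion, although the stated rule would make them failures. No planned analysis restores them.

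The number is probably small. Under the assumed 18/33 and 10/33, losing one per arm changes the difference by 0.8 points; losing two in one arm only changes it by +3.5 or −2.0 points. The response rates, the early-loss counts and their split by arm are all assumptions. The 18% in the plan covers dropout and missing data together and says nothing about timing.

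It would be tempting to say that the exclusion favours etokimab. The documents do not show that: removal on active raises the estimated effect, removal on placebo lowers it, and nothing indicates which would be commoner. The co-primary analyses are not affected. This is an inexpensive improvement to two secondary endpoints, not a flaw that threatens the trial's main conclusion.

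**What to change.** In SAP 8.2.2 and 8.2.3, name the population explicitly: all randomised subjects who received at least one dose and have a baseline score, analysed as randomised, with a missing Week 16 score counted as non-response. Keep the FAS for the repeated-measures analyses. Record the departure from Protocol 9.3 and 9.4.2.2 in SAP Section 12, and report by randomised arm how many dosed subjects the FAS excludes.

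If the sponsor prefers not to change the pre-specified population, the least that would do is to run this as a sensitivity analysis, or to state that the non-responder rule applies only within the FAS, and in either case to report the exclusions by arm.

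The cost is SAP text and one documented change from the protocol. No new data are needed. Response rates will be slightly lower in any arm that has such subjects.
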